9.3. Facilitation of data returns

Every month the central team will send reminders to clinical teams on each site for any new cases that need reporting. Further, for cases where part one of the CRF has already been submitted, the central team will send reminders to sites after four weeks, and another reminder two weeks later. If there is still no response after a further three weeks, the clinician will be contacted by telephone.

9.4. Follow up

Until discharge, or death, or 30 days after whole blood transfusion - whichever occurs first.

9.5. End of study definition

Two years after starting the transfusion of RC&Plasma component at RLH.

10. Statistical considerations

10.1. Sample size

Primary Outcome:

The primary outcome is the percentage of occasions per annum where component was delivered as specified and as scheduled or requested from hospital. It has been agreed between RLH and NHSBT that RC&Plasma component will not be delivered during bank holidays, and in these days 'On-time-in-full' calculation will be excluded. The current NHSBT OTIF standard is 98%. The study will be declared feasible if OTIF is achieved in at least 97.3% (95%CI: 95.7% - 98.4%).

The criteria for progression on wastage level is given under section 13.3 below.

Secondary Outcomes:

Since March 2012 when the Royal London team started carrying RBC on board, on average 70 patients per year have been transfused an average of 2 units of RBC in the pre-hospital setting. We therefore project that around 140 patients will be transfused with a RC&Plasma component during the study period (24 months). Based on The London ambulance data analysis of patients, approximately 70% of trauma patients who receive a RBC transfusion arrive in emergency department with a Base Deficit >6 mEq/L. Assuming a retrospective cohort of approximately 160 patients and at least 60 patients in the RC&Plasma arm, the study will have 80% probability (power) at 5% level of significance of detecting an absolute 20% reduction in the proportion of patients arriving in emergency department with a Base Deficit >6 mEq/L in the RC&Plasma group. The required sample size is attainable even after postulating a loss-rate of 25% (e.g. blood samples not being taken due to patients dying etc.).

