In March 2012 for the first time in the UK, the Royal London Hospital allowed the pre-hospital team to transfuse RBC on-scene to trauma patients who were bleeding: this has contributed to reduction in the pre-hospital mortality from 42% in 2009 to 27% in 2015 (p <0.01). However, in the pre-hospital setting the logistics of delivering FFP in addition to RBC could be quite challenging as this would: a) necessitate additional weight for the pre-hospital personnel approaching the scene of the accident; b) increase the complexity of resuscitating patients because several bags (blood and fluid) would need to be administered to a patient who may not have enough intravenous access, and clinical team are occupied doing other important tasks; and b) delay the transfer of patients to hospital because clinical team would attempt to transfuse both RBC and FFP at the scene, which could be potentially detrimental to outcome (Meyer, et al 2017). While some trauma centres like Newcastle and Oxford have decided to transfuse RBC and FFP in the pre-hospital setting, clinicians realise that a single whole blood (WB) product that contains everything in one bag (RBC, FFP and Platelets) would be ideal, but this is not yet possible in the UK due to current manufacturing procedures removing platelets from WB donations. Another product that contains RBC and FFP in one bag (RC&Plasma thereafter) is available in the UK, and has been used in the past, but it is not currently in routine use. Moreover, studies comparing its efficacy and safety, against standard blood components have not been conducted.

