6.4. Secondary endpoint

To evaluate the clinical impact of RC&Plasma transfusion versus RBC transfusion and RBC and FFP transfusion, the following clinical data will be collected:

- Changes in base deficit and prothrombin time from scene to emergency department
- Transfusion wastage (red blood cells, fresh frozen plasma, platelets, cryoprecipitate) at 24-hours post injury
- Transfusion requirement at 24 hours and up to hospital discharge or 28 days, or death whichever occur first
- Total hospital length of stay
- Survival analysis up to 24-hours and 28 days post injury

Other factors that will be monitored include: *NHSBT*

- Wastage (units per month)
- Substitutions (units per month)
- Impact on supply of other blood components
- Impact on other processes
- Additional administration resources and time required to provide RC&Plasma

Hospital

- Additional administration support and time required to support clinical team
- % of RC&Plasma used in the pre-hospital setting
- % of RC&Plasma used in emergency department

7. Study population

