9.1. Case Identification

In the UK, it is a legal requirement that all hospital blood transfusion laboratories have a system in place to document the final destination of every blood component issued, so that any probable recipient-related transfusion complications (e.g. infections) can be traced back to donors, so that appropriate measures can be taken (BSQR 2005). These records must be kept in the transfusion laboratories for 30 years.

Therefore, all cases will be identified from the transfusion laboratories at three sites - the RoyaL London Hospital (RLH), John Radcliffe Hospital, Oxford and Royal Victoria Infirmary,

Newcastle Hospital. The RLH supplies blood to pre-hospital team for whole of London, and therefore RLH laboratory will keep records of all units issued and transfused (see diagram below).

Transfusion laboratories will only inform the central team at Barts Health of the date/time when blood was transfused in the pre-hospital setting, the name of hospital that the patient was admitted to, and the unique donation number of the transfused units. No patient' identifiers will be given to the central team. Once the central team has been informed of the case, the clinical team on the relevant site will be contacted and asked to submit the case report form (CRF) for the identified case using patient's case notes.

Study Scheme Diagram

Transfusion form handed over from Trauma Team to transfusion laboratory

Cases identified from the transfusion laboratory

Case report form completed by clinical team at:

a) 24 hours and b) 30 days, or discharge or death – whichever occurs first

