10.2. Method of analysis

Statistical analyses will be performed using STATA (StataCorp, USA). Categorical variables will be tabulated as frequencies and percentages and compared using Fisher's exact tests; continuous variables will be summarised as means [standard deviation] or medians [interquartile range] and compared using t-tests or non-parametric equivalents. All tests will be two-sided at the 5% level of significance. Multivariable regression models will be used to examine the association between treatment groups (RC&Plasma versus RBC-only transfusions) and various clinical outcomes, controlling for potential confounders (including but not limited to: type and location of injury; age; other co-morbidities) as appropriate.

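### Base deficit is compared only in patients who live to give an ED sample, and nobody is named to complete the CRF for a transfused patient who dies before admission

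*Protocol*

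**What the plan says.** **Outcome.** Protocol 10.1 powers the main clinical comparison on the proportion arriving in the ED with base deficit above 6 mEq/L. The control rate is that "approximately 70% of trauma patients who receive a RBC transfusion arrive in emergency department with a Base Deficit >6 mEq/L," and with about 160 RBC and at least 60 RC&Plasma patients "the study will have 80% probability (power) at 5% level of significance of detecting an absolute 20% reduction." The endpoint listed in 6.4 is the change in base deficit from scene to ED. Both need a patient who is alive and sampled in the ED.

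**Deaths.** Section 10.1 states that the required sample size is "attainable even after postulating a loss-rate of 25% (e.g. blood samples not being taken due to patients dying etc." It does not divide the 25% between deaths and other losses, or between cohorts.

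**Entry.** Section 7.1 admits RC&Plasma patients once a unit has been started pre-hospital. The RBC cohort is defined by pre-hospital transfusion in London, with a bracketed mention of the RLH emergency department. Section 7.2 lists no exclusions.

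**Reporting.** Under 9.1 cases are found from transfusion laboratory records. The laboratory passes on the date and time of transfusion, "the name of hospital that the patient was admitted to, and the unique donation number of the transfused units." The clinical team at the relevant site then completes the CRF from case notes. Part 1 of the CRF (Table 1, section 9.2) asks for time of death in hours from administration, and its cause. Section 6.4 lists "Survival analysis up to 24-hours and 28 days post injury."

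**The concern.** Death before ED sampling is the worst result a pre-hospital transfusion can have, and both treatment and calendar period may influence it. Counting it as sample loss removes those patients from the denominator. If one strategy brings more of the sickest patients alive to the ED, they arrive with high base deficits and that strategy looks worse. If it loses more of them, it looks better.

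The regression in 10.2 adjusts for baseline confounders. It cannot supply an outcome for someone who died before it could be measured. The main comparator is historical, so the documents give no ground for assuming that early death is equal in the two cohorts.

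The second strand concerns data capture. A patient who dies at scene has no admitting hospital, and section 9.1 does not say who fills in the form. If these deaths are captured unevenly across the three cohorts, the survival comparison is affected as well. The study is meant to prepare a trial of efficacy and safety, so distorted estimates would carry forward.

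**Working it through.** **1. The plan's own figure.** Inputs from 10.1: 70% vs 50%, 160 RBC, 60 RC&Plasma. From 10.2: "All tests will be two-sided at the 5% level of significance." Normal approximation: power = Φ[(|p1 − p2| − 1.96·SE0)/SE1].
- Pooled p = (112 + 30)/220 = 0.6455
- SE0 = √[0.6455 × 0.3545 × (1/160 + 1/60)] = 0.0724
- SE1 = √[0.21/160 + 0.25/60] = 0.0740
- Power = Φ[(0.20 − 0.1419)/0.0740] = 78.4%

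This is close enough to the stated 80%. With the planned test (proportions are to be "compared using Fisher's exact tests") exact power is 75.9%. The stated figure reproduces, so the issue is what is being estimated, not the power arithmetic.

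**2. Bias with no other effect.** The early-death rates here are assumptions. Let d0 and d1 be the proportions dying before the ED sample in the RBC and RC&Plasma cohorts. RBC survivors have 70% above 6. Patients who would survive under either strategy keep 70%, and every additional survivor arrives above 6.

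Observed RC&Plasma proportion = [(1 − d0) × 0.70 + (d0 − d1)]/(1 − d1)

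| d0 | d1 | RC&Plasma survivors above 6 | Against 70% |
|---|---|---|---|
| 25% | 20% | 0.575/0.80 = 71.9% | looks 1.9 points worse |
| 25% | 15% | 0.625/0.85 = 73.5% | looks 3.5 points worse |
| 25% | 10% | 0.675/0.90 = 75.0% | looks 5.0 points worse |

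If only 90% of the additional survivors arrive above 6, the first two rows become 1.2 and 2.4 points.

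In reverse, RC&Plasma has more early deaths, all taken from patients who would have arrived above 6:
- 20% vs 25%: (0.80 × 0.70 − 0.05)/0.75 = 68.0%, so it looks 2.0 points better.
- 15% vs 25%: (0.85 × 0.70 − 0.10)/0.75 = 66.0%, so it looks 4.0 points better.

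With d0 = d1 the bias is zero.

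**3. Dilution of a true effect.** Take d0 = 25%, and a real fall from 70% to 50% in those who survive either way. Observed = [(0.75 × 0.50) + (0.25 − d1)]/(1 − d1).

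| d1 | Observed RC&Plasma | Observed effect | Power at 160/60 |
|---|---|---|---|
| 20% | 53.1% | 16.9 points | 64.6% |
| 15% | 0.475/0.85 = 55.9% | 14.1 points | 50.4% |
| 10% | 58.3% | 11.7 points | 37.7% |

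The projected numbers are larger than 160/60. After 25% loss, 140 × 0.75 = 105 RC&Plasma and 200 × 0.75 = 150 RBC patients remain. The full 20-point effect then has 90.0% power. The diluted 14.1-point effect has Φ[(0.1412 − 1.96 × 0.0610)/0.0612] = 63.8%.

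**4. Why three ordered levels and not a two-way composite.** In step 2, death or base deficit above 6 is 0.25 + 0.75 × 0.70 = 77.5% for RBC. For RC&Plasma at d1 = 15% it is 0.15 + 0.85 × 0.735 = 77.5%. The composite removes the false harm but gives no credit for the deaths avoided. Ranking death below base deficit above 6 does.

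**5. The reporting route.** Section 7.1 makes scene deaths eligible. Section 9.1 makes them detectable through the unit records, and Table 1 gives them a field. Only the person who completes the form is unspecified when there is no admission.

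**The case against.** **The 25% is an attainability allowance, not an analysis rule, and an SAP may deal with deaths.** This is fair: 10.1 uses the figure only to say that the numbers can be reached, and 10.2 does not say that deaths are dropped. But the ED-arrival definition is written into 6.4 and 10.1, and no SAP can recover data that the CRF route did not collect.

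**The bias is small and rests on assumed rates.** This stands. At 150/105 the standard error of the difference, with 70% in both cohorts, is √[0.21 × (1/150 + 1/105)] = 5.8 points, so a 2-4 point bias lies inside sampling error. Requiring every additional survivor to arrive above 6 is an extreme case. Dilution of a real effect matters more.

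**Consequences are limited.** The primary endpoints are on-time delivery and wastage, and no progression criterion in 10.3 uses base deficit or mortality. Survival is also reported separately. This limits the weight of the point without removing it.

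**Stronger readings that the documents do not support:**
- *The 25% allowance is too low because pre-hospital mortality is 27%.* Section 5.1.1 reports a "reduction in the pre-hospital mortality from 42% in 2009 to 27% in 2015 (p <0.01" but does not say this is the rate among transfused patients. Its 2009 value predates pre-hospital RBC, which began in March 2012, so the series cannot be restricted to them.
- *Deaths leave the comparison underpowered.* After the stated loss 105 RC&Plasma patients remain against 60 needed. The 150 RBC patients fall slightly short of 160, yet power for the planned effect is 90.0%.
- *Scene deaths cannot be reported, so the survival analysis omits them.* The unit records and the CRF death field say otherwise. Losing them is a risk inferred from 9.1, not something the protocol states.

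**Conclusion.** The concern holds in a limited form. As written, the base deficit comparison is conditional on survival to an ED sample, although patients enter at transfusion. It is biased whenever early death differs between cohorts.

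The size depends on rates the documents do not give. For assumed differences of 5 to 10 points, the bias is about 2 to 4 points in either direction when there is no other effect. With early death of 25% vs 15%, a true 20-point effect shrinks to about 14. With equal early death there is no such bias.

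The gap in 9.1 is procedural: nobody is assigned to complete the form for a patient who was never admitted. Neither strand affects the feasibility endpoints. Both should be corrected because the clinical comparison is meant to inform a later trial.

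**What to change.** **Sections 6.4 and 10.2.** Keep the ED-arrival proportion. Beside it, report an ordered outcome in all transfused patients: died before ED sample (worst), alive with base deficit above 6, alive with base deficit 6 or below. Tabulate deaths before sampling by cohort, separately from samples missing for other reasons.

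**Section 9.1.** Name who completes CRF Part 1, from existing pre-hospital records, when a transfused patient dies before admission. Apply this in all three cohorts, and count these deaths in the 24-hour and 28-day survival analyses.

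**Cost.** Some retrospective look-up for the 2015-2018 cohort. There is also a loss of power if treatment does not affect early death. As a guide, take the related two-way composite (death or base deficit above 6), equal early death in both cohorts, and 70% vs 50% in survivors:
- 10% early death: 73.0% vs 55.0%, power 71.6% at 160/60 and 93.0% at 200/140.
- 25% early death: 77.5% vs 62.5%, power 60.5% at 160/60 and 85.0% at 200/140.

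This is a reason to report the two analyses together rather than replace one with the other.

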10.2. Method of analysis

Statistical analyses will be performed using STATA (StataCorp, USA). Categorical variables will be tabulated as frequencies and percentages and compared using Fisher's exact tests; continuous variables will be summarised as means [standard deviation] or medians [interquartile range] and compared using t-tests or non-parametric equivalents. All tests will be two-sided at the 5% level of significance. Multivariable regression models will be used to examine the association between treatment groups (RC&Plasma versus RBC-only transfusions) and various clinical outcomes, controlling for potential confounders (including but not limited to: type and location of injury; age; other co-morbidities) as appropriate.

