Objectives / aims	Secondary objectives Compare the impact of RC&Plasma transfusion with red blood cell (RBC) transfusion (retrospective data) and RBC and fresh frozen plasma (FFP) transfusion (prospective data from Newcastle and Oxford hospital) on: resuscitative effect (base excess, lactate), coagulation parameters, overall transfusion requirement, haemolysis, days in hospital and mortality, in trauma bleeding patients.			
Number of participants	140 in the RC&Plasma arm 200 in the RBC arm (retrospective) 150 in the RBC and FFP arm			
Inclusion and exclusion criteria	 Inclusion criteria All trauma patients requiring pre-hospital major haemorrhage protocol activation by the pre-hospital team because of haemorrhagic shock and for whom clinician has transfused a RC&Plasma component (in London), or RBC and FFP by either the Great North or Thames Valley Air Ambulance. Patients who have received at least one RBC unit in the pre-hospital setting because of trauma haemorrhage between March 2015 and April 2018 (retrospective cases) 			
Study duration	2 years			

5. Introduction

Uncontrolled bleeding due to trauma is associated with significant morbidity and mortality, and substantial costs to NHS. Early administration of fresh-frozen-plasma (FFP) and platelets in a high (near 1:1:1) ratio with red blood cells (RBC) reduces mortality, and this has now become standard of care for trauma patients who are bleeding. However, the logistics of delivering FFP together with RBC in the pre-hospital setting could delay transfer to hospitals (which could be detrimental), and also place additional demands on the clinical team. Availability of a component that contains red cells and plasma (RC&Plasma) in a single bag could overcome these challenges. Such component is available in the UK: however, it is not used routinely. Furthermore, the efficacy and safety relative to other transfusion strategies have not been investigated in randomised controlled trials.

The Royal London Hospital Major Trauma Service and the Helicopter Emergency Medical Service, have made a clinical decision to change standard treatment for the management of trauma patients who are bleeding in the pre-hospital setting, from the transfusion of RBC to the transfusion of RC&Plasma for 24 months.

The overall objectives of this project are to:

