6.2. Secondary objective

Compare the impact of RC&Plasma transfusion with RBC transfusion (retrospective data between March 2015 to April 2018) and RBC and FFP transfusion (prospective data from Newcastle and Oxford hospital) on: resuscitative effect (base excess, lactate), coagulation parameters, overall transfusion requirement, haemolysis, days in hospital and mortality, in trauma bleeding patients.

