7.2. Exclusion criteria

None

8. Study design

Feasibility, observational cohort study.

RC&Plasma transfusion will replace RBC transfusion in the pre-hospital setting in London, and will be available for transfusion in hospital at RLH for trauma patients >1yrs old. Operational and clinical data relating to administration of RC&Plasma component will be compared with historical data of RBC transfusion in the pre-hospital setting in London from March 2015 to April 2018.

Newcastle and Oxford hospitals will continue to administer RBC and FFP transfusion in the pre-hospital setting.

9. Study procedures

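### The confounder-adjusted models in section 10.2 cover only RC&Plasma versus RBC-only, although the protocol also commits to comparing RC&Plasma with the prospective RBC and FFP cohort

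*Protocol*

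**What the plan says.** **What is promised.** The secondary objective (6.2) compares RC&Plasma with retrospective RBC data and also with "RBC and FFP transfusion (prospective data from Newcastle and Oxford hospital) on: resuscitative effect (base excess, lactate), coagulation parameters", among other outcomes. Section 6.4 repeats both comparators: "To evaluate the clinical impact of RC&Plasma transfusion versus RBC transfusion and RBC and FFP transfusion, the following clinical data will be collected". The synopsis and overall objective b in the Introduction make the same commitment. The synopsis plans "140 in the RC&Plasma arm" and "150 in the RBC and FFP arm", and section 7.1 defines the latter as a comparator cohort.

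**What is specified for analysis.** Section 10.2 has two layers. The general layer names no groups: "Categorical variables will be tabulated as frequencies and percentages and compared using Fisher's exact tests", with t-tests or non-parametric equivalents for continuous variables. The adjusted layer does name its groups. It concerns the "association between treatment groups (RC&Plasma versus RBC-only transfusions) and various clinical outcomes, controlling for potential confounders", and the list of confounders that follows is expressly open-ended.

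**Elsewhere.** The comparison sentence in section 8 covers only the historical cohort: "Operational and clinical data relating to administration of RC&Plasma component will be compared with historical data of RBC transfusion". Section 8 does also record that Newcastle and Oxford go on giving RBC and FFP. The power statement in 10.1 concerns only RC&Plasma against the retrospective RBC cohort.

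**The concern.** The protocol states two clinical contrasts and gives confounder control to one of them. The parenthesis that defines the treatment groups is not introduced as an example, whereas the confounder list in the same sentence is left open. As written, the adjusted contrast is therefore fixed more narrowly than the secondary objective it serves.

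The contrast left out needs adjustment at least as much as the one included. RC&Plasma is given in London; the RBC and FFP patients come through the Great North and Thames Valley services to Newcastle and Oxford. Differences in injury pattern, severity or transfer between these regions could appear in a crude comparison as differences between components.

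This is also the only concurrent comparator: the RBC data end in April 2018 and RC&Plasma starts in June 2018. It is the only comparator that contains plasma. A crude result could therefore carry weight when the future trial is designed.

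**Working it through.** **Step 1. Commitments against methods.**

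| Place in protocol | RC&Plasma v RBC | RC&Plasma v RBC and FFP |
|---|---|---|
| Synopsis; objective b; 6.2; 6.4 | yes | yes |
| Section 8, comparison sentence | yes | not named |
| 10.1, power statement | yes | not named |
| 10.2, unadjusted tests | no groups named | no groups named |
| 10.2, multivariable models | yes | not named |

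No other section gives an adjusted method for the RBC and FFP cohort.

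**Step 2. The protocol's own figure.** Section 10.1 states 80% power for 70% v 50% with Base Deficit >6 mEq/L, 160 RBC v 60 RC&Plasma, at the 5% level (two-sided in 10.2). By the normal approximation:

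- pooled p = (160×0.70 + 60×0.50)/220 = 0.6455
- SE0 = √[0.6455×0.3545×(1/160 + 1/60)] = 0.0724
- SE1 = √[0.70×0.30/160 + 0.50×0.50/60] = 0.0740
- z = (0.20 − 1.96×0.0724)/0.0740 = 0.784, so power = Φ(0.784) = 78.4%

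This is close enough to count as reproduced (exact enumeration with Fisher's test gives 75.9%). The figure concerns the RBC contrast only, and nothing in this point changes it.

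**Step 3. Illustration of what a crude comparison could do.**

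Inputs from the protocol: 140 and 150 patients (synopsis); 25% loss and a 70% rate of Base Deficit >6 mEq/L (10.1); two-sided 5% (10.2). Evaluable: 140×0.75 = 105 and 150×0.75 = 112.5, taken as 112.

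Assumptions not in the protocol: no treatment effect, and a case-mix gap of 5, 10 or 15 points in the RBC and FFP cohort.

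Normal approximation for 70% (n=105) v 60% (n=112):

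- pooled p = (73.5 + 67.2)/217 = 0.6484
- SE0 = 0.0649, SE1 = 0.0644
- z = (0.10 − 1.96×0.0649)/0.0644 = −0.42, so the probability of rejection is about 34%

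For Fisher's test, the one named in 10.2, the probability is the sum of Bin(x; 105, p1)×Bin(y; 112, p2) over all tables with p ≤ 0.05:

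| Assumed rates | Fisher's test rejects |
|---|---|
| 70% v 70% | 4.1% |
| 70% v 65% | 10.6% |
| 70% v 60% | 31.5% |
| 70% v 55% | 60.6% |

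With the 10-point gap in the other direction (60% v 70%) the figure is 32.2%, so direction hardly matters.

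**The case against.** **An analysis plan not shown here may cover it.** It may. But the protocol does not leave the adjusted contrast open for a later document; it specifies it. A plan that followed 10.2 would omit the RBC and FFP contrast, and one that included it would depart from 10.2. The mismatch stands.

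**A reader might infer that the protocol assigns the RBC and FFP cohort to unadjusted tests.** It does not say so, because 10.2 attaches no groups to those tests. What can be said is that no adjusted analysis is specified for this contrast and that the unadjusted tests are the only methods left.

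**A reader might also infer that the confounder list wrongly omits injury severity.** The documents do not support this. The list is open-ended, and Table 1 collects severity, so nothing prevents its use. Nor do they support adjusting for a scene laboratory value. Table 1 does not say that the scene sample precedes transfusion; if it does not, adjustment could remove part of the treatment effect.

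**The size is hypothetical.** This is correct. The protocol gives no Base Deficit rate for the RBC and FFP cohort and no case-mix difference, so the rejection rates follow from the gap chosen. I give no mortality illustration: the 27% in section 5.1.1 is London pre-hospital mortality in 2015, whereas the endpoint is survival to 24 hours and 28 days.

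**Adjustment cannot rescue the contrast fully.** This is also correct. Component type coincides with region and service, so confounding tied to either cannot be modelled away. That argues for saying so, not for leaving measured confounders uncontrolled.

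**It is secondary.** This holds too. The primary endpoints are OTIF delivery and wastage, and no progression criterion in 10.3 depends on a between-cohort clinical comparison. Likewise, the protocol describes the future trial only as comparing different transfusion strategies; it does not single out RC&Plasma against RBC and FFP.

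**Conclusion.** The point holds as an inconsistency of scope. Section 10.2 limits the adjusted models to RC&Plasma versus RBC-only, while four places in the protocol also commit to a comparison with the RBC and FFP cohort, for which no adjusted analysis is given. Followed as written, a stated secondary objective with 150 planned patients would rest on crude comparisons between regions.

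The size cannot be fixed from the protocol. Under the assumptions shown (no treatment effect, 105 v 112 evaluable, a 10-point case-mix gap from 70%), Fisher's test would reject about 31% of the time; gaps of 5 and 15 points give about 11% and 61%. These figures should not be read as the expected error, nor should the nominal 5% be read as what adjustment would restore.

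Severity is moderate. Only secondary outcomes are touched; the OTIF threshold, wastage and progression criteria are unaffected.

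**What to change.** 1. In 10.2, extend the multivariable models to both contrasts: RC&Plasma v RBC-only, and RC&Plasma v RBC and FFP. A three-level treatment factor or two pairwise models would serve equally well.
2. Use confounders already collected in Table 1, such as severity of injury. Do not adjust for a scene laboratory value unless it is confirmed that the sample precedes transfusion.
3. State in 10.2 that treatment coincides with region and air ambulance service in the RBC and FFP contrast, so residual confounding remains after adjustment.
4. Add the RBC and FFP comparison to the comparison sentence in section 8.

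The cost is a few sentences and a little extra analysis. No new patients or data items are needed. The change should be made before analysis, so that the adjusted contrast is pre-specified.
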